For the current study, the following individuals, funding, and/or regulatory agencies will be notified (choose those that apply):

- All Co-Investigators listed on the protocol.
- Yale Cancer Center Data and Safety Monitoring Committee (DSMC)
- National Institutes of Health
- Food and Drug Administration (Physician-Sponsored IND # \_\_\_\_\_)
- Medical Research Foundation (Grant \_\_\_\_\_)
- Study Sponsor
- Other Data Safety Monitoring Board (DSMB) or Committee (DSMC)

The principal investigator [name] will conduct a review of all adverse events upon completion of every study subject. The principal investigator will evaluate the frequency and severity of the adverse events and determine if modifications to the protocol or consent form are required.

- d. For multi-site studies for which the Yale PI serves as the lead investigator: This is a single site study
  - i. How will adverse events and unanticipated problems involving risks to subjects or others be reported, reviewed and managed?
  - ii. What provisions are in place for management of interim results?
  - iii. What will the multi-site process be for protocol modifications?

**12. Statistical Considerations:** Describe the statistical analyses that support the study design.

*All data will be collected prospectively. Preoperative data will include patient demographics, number of previous URS, baseline medications including analgesics, urine culture, stone size and location, and pain questionnaire scores. Mean scores will be calculated and compared between groups stratified by follow-up time. The number of adverse events and hospital admissions related to pain will recorded and described as counts and percentages. The primary outcome that will be used to estimate effect size is mean post-operative pain.*

*Our study is set up as two independent groups with a continuous outcome (Pain measured on a 1-10 scale) and an enrollment ratio of 1. We anticipate mean post-operative pain in the non-intervention group to be 7 with a standard deviation of 2. We aim to detect a 10% difference in pain, in the intervention arm. With an alpha of 0.05 and a power of 80% we will need to enroll 63 patients in each arm.*

SECTION VI: RESEARCH INVOLVING DRUGS, BIOLOGICS, RADIOTRACERS, PLACEBOS AND DEVICES
--

*If this section (or one of its parts, A or B) is not applicable, state N/A and delete the rest of the section.*

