**SECTION VII: RECRUITMENT/CONSENT AND ASSENT PROCEDURES**

**1. Targeted Enrollment: Give the number of subjects:**

- a. targeted for enrollment at Yale for this protocol 126  
b. If this is a multi-site study, give the total number of subjects targeted across all sites N/A

**2. Indicate recruitment methods below.** Attach copies of any recruitment materials that will be used.

- |   |   |                                     |
|---|---|-------------------------------------|
|  Flyers   |  Internet/Web Postings                                      |  Radio      |
|  Posters  |  Mass E-mail Solicitation                                   |  Telephone  |
|  Letter   |  Departmental/Center Website                                |  Television |
|  Medical Record Review  |  Departmental/Center Research Boards                        |  Newspaper  |
|  Departmental/Center Newsletters  |  Web-Based Clinical Trial Registries                        |                                     |
|  YCCI Recruitment database  |  Clinicaltrials.gov Registry (do not send materials to HIC) |                                     |
|  Other (describe): Patients will be recruited at time of consultation for URS |   |                                     |

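### 63 per arm gives about 50% power, not 80%, for a 10% reduction from a mean of 7 with SD 2; it fits a 1.0-point (14%) difference

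*Combined protocol and SAP*

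**What the plan says.** The whole justification is in Section V, item 12 (Statistical Considerations). The design is "two independent groups with a continuous outcome (Pain measured on a 1-10 scale) and an enrollment ratio of 1". The control-arm assumption is: "We anticipate mean post-operative pain in the non-intervention group to be 7 with a standard deviation of 2". The next sentence sets the target: "We aim to detect a 10% difference in pain, in the intervention arm". The result follows: "With an alpha of 0.05 and a power of 80% we will need to enroll 63 patients in each arm".

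Section VII, item 1 carries the number forward, with the figure "targeted for enrollment at Yale for this protocol 126". That is 2 × 63, so nothing is added for missing scores.

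The protocol does not give the target difference in points, does not say what the 10% is a percentage of, and does not say whether the test is one-sided or two-sided.

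**The concern.** The 10% sentence comes straight after the control mean of 7 and names no other base, so the natural reading is 7.0 versus 6.3. That is a standardised difference of 0.7 / 2 = 0.35, and 63 per arm is far too few for 80% power at that size.

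This is the only power statement for the primary outcome. A reader who takes it at face value will believe the trial has an 80% chance of detecting a 10% reduction. Section IX (Potential Benefits) says that a negative study would argue against using the drug in this setting. That is not a formal decision rule, but it shows how a null result would be read. If a true 0.7-point benefit is missed about half the time, a null result cannot support that reading.

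**Working it through.** **Inputs** (all from Section V, item 12): control mean 7; SD 2, taken as common to both arms; 1:1 allocation; alpha 0.05; power 80%; 63 per arm. Two-sided testing is assumed first because sidedness is not stated.

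**Formula.** Normal approximation for two means: n per arm = 2 × SD² × (z₁₋α/₂ + z₁₋β)² / δ². With SD = 2, z = 1.960 and z = 0.842, the numerator is 2 × 4 × 7.849 = 62.79, so n = 62.79 / δ².

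**Reproducing the plan's 63.** With δ = 1.0, n = 62.79 / 1.00 = 62.8, rounded up to 63. This matches exactly. A 1.0-point difference is 1.0 / 7 = 14.3% of the control mean.

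**The stated target.** With δ = 0.10 × 7 = 0.7, n = 62.79 / 0.49 = 128.1, rounded up to 129 per arm (258 in total). The t-test calculation gives 129.1, so 130 per arm (260 in total).

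**Other readings of the text**

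| Reading | δ (points) | n per arm, normal (t-test) | Power at 63 per arm (t-test) |
|---|---|---|---|
| 10% of 7, two-sided | 0.7 | 129 (130) | 49.6% |
| 10% of 7, one-sided | 0.7 | 101 (102) | 62.1% |
| 10% of the 1-to-10 range (9 points), two-sided | 0.9 | 78 (79) | 70.7% |
| 10% of the 1-to-10 range, one-sided | 0.9 | 62 (62) | 80.7% |
| 10% of a maximum of 10, two-sided | 1.0 | 63 (64) | 79.5% |

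The one-sided rows use (1.645 + 0.842)², so n = 49.46 / δ². Two more versions of a 10% relative difference were tried, both two-sided. Taking 7 as 90% of the other mean (δ = 7/0.9 − 7 = 0.78) gives 104 per arm. A log-scale comparison with coefficient of variation 2/7 gives 111. No version of a 10% difference relative to 7 gives 63.

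**What 63 per arm can detect.** At 80% power the smallest detectable difference is 1.01 points by t-test, or 14.4% of 7. For 63 per arm to give 80% power at 0.7 points, the SD would have to be 1.39 instead of 2.

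**Precision.** The expected 95% CI half-width is t(0.975, 124) × 2 × √(2/63) = 1.979 × 0.356 = 0.705 points. An observed difference of exactly 0.7 would therefore just miss significance. Any non-significant result that favours ketorolac would leave 0.7 inside the interval.

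**Missing scores (illustration only).** The protocol gives no missing-data rate. If 10% of scores were missing, about 57 per arm would remain (63 × 0.9 = 56.7), and power would be 46% for 0.7 points and 75% for 1.0 point.

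**The case against.** The strongest reply is that the authors meant 10% of a 10-point scale. The protocol speaks only of a difference in pain, it names the scale two sentences earlier, and 1.0 point reproduces 63 exactly. On that view the arithmetic is right and the fault is an undefined effect size. This is probably where 63 came from. It does not clear the text, because nothing in the paragraph says the percentage refers to the scale. A tenth of the stated 1-to-10 range would in any case be 0.9 points, which needs 78 or 79 per arm two-sided.

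A second reply is that sidedness is not declared, and a one-sided test for 0.9 points needs 62 per arm, close to 63. That is true, so 1.0 point is the only match among two-sided readings and not among all conceivable ones. The one-sided route needs two unstated choices and still does not describe a 10% reduction from 7.

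The missing-data figures rest on an assumed rate. The protocol does not fix the primary time point, so likely missingness cannot be judged. The main finding does not depend on them.

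**Conclusion.** The concern holds: the power statement is wrong as written. On the natural reading (0.7 points, common SD 2, two-sided alpha 0.05), the trial has about half the patients it needs (63 against 129 or 130 per arm), and its power is about 50% instead of 80%. A one-sided test raises that only to about 62%. If 1.0 point was intended, the number of patients is adequate for that target (79.5% by t-test, 80.1% by the normal formula), but the protocol misdescribes the effect as 10% when it is 14% of the assumed control mean. Either way the paragraph must be corrected, because the stated mean, SD, percentage, power and sample size do not agree. The SD of 2 and the mean of 7 are taken from the protocol as given.

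**What to change.** Keep the total at 126 and replace the target and sample-size sentences in Section V, item 12 with a statement to this effect:

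> With 63 patients per arm, SD 2 and a two-sided alpha of 0.05, the trial has 80% power to detect a difference of 1.0 point in mean pain (7.0 versus 6.0, a 14% relative reduction). Power for a 10% (0.7-point) difference is about 50%. The difference in means will be reported with its 95% confidence interval, and a non-significant result will not be taken to exclude a 10% benefit.

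This costs a few sentences and no patients. The price is a less favourable, but true, statement of what the trial can detect.

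If the investigators decide that 0.7 points is the difference they need to detect, restating the text is not enough. The sample size then has to rise to 129 or 130 per arm (258 to 260 in total), before any allowance for missing scores, and the enrolment target in Section VII, item 1 has to change with it.

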Following the procedure, patients will rate their pain using a visual pain assessment scale at 1 hour postoperatively and at the time of discharge from the recovery room. Once the patient is at home, they will fill out a validated survey that has questions related to pain. This will be filled out once a day for a total of 7 days following the procedure. In addition, we will provide a medication utilization diary sheet for the patient to record daily use of prescribed narcotic and other as needed over the counter medications such as acetaminophen and ibuprofen. This will also be done daily for a total of 7 days. The patient will be surveyed at their one-week postoperative visit using the same assessment. All adverse drug reactions will be recorded from time of administration to initial follow-up. The following is the study schedule:

Study Schedule	Preop	Intraop	1hr post op	2 hr post op	1 week
Assessments					
Consent	x				
History and Physical	x				
Urine Culture					
Post URS medication record			x	x	
Pain Questionnaire	x		x	x	x
Adverse Events		x	x	x	x

4. Genetic Testing N/A

A. Describe

- i. the types of future research to be conducted using the materials, specifying if immortalization of cell lines, whole exome or genome sequencing, genome wide association studies, or animal studies are planned
- ii. the plan for the collection of material or the conditions under which material will be received
- iii. the types of information about the donor/individual contributors that will be entered into a database
- iv. the methods to uphold confidentiality

B. What are the conditions or procedures for sharing of materials and/or distributing for future research projects?

C. Is widespread sharing of materials planned?

D. When and under what conditions will materials be stripped of all identifiers?

E. Can donor-subjects withdraw their materials at any time, and/or withdraw the identifiers that connect them to their materials?

- i. How will requests to withdraw materials be handled (e.g., material no longer identified: that is, anonymized) or material destroyed)?

F. Describe the provisions for protection of participant privacy

G. Describe the methods for the security of storage and sharing of materials

5. **Subject Population:** Provide a detailed description of the types of human subjects who will be recruited into this study.

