**Choose one:**

- For entire study
- For recruitment purposes only
- For inclusion of non-English speaking subject if short form is being used

- i. Describe why it would be impracticable to obtain the subject's authorization for use/disclosure of this data;
- ii. If requesting a waiver of **signed** authorization, describe why it would be impracticable to obtain the subject's signed authorization for use/disclosure of this data;

**By signing this protocol application, the investigator assures that the protected health information for which a Waiver of Authorization has been requested will not be reused or disclosed to any person or entity other than those listed in this application, except as required by law, for authorized oversight of this research study, or as specifically approved for use in another study by an IRB.**

*Researchers are reminded that unauthorized disclosures of PHI to individuals outside of the Yale HIPAA-Covered entity must be accounted for in the "accounting for disclosures log", by subject name, purpose, date, recipients, and a description of information provided. Logs are to be forwarded to the Deputy HIPAA Privacy Officer.*

- 7. Required HIPAA Authorization:** If the research involves the creation, use or disclosure of protected health information (PHI), separate subject authorization is required under the HIPAA Privacy Rule. Indicate which of the following forms are being provided:

- Compound Consent and Authorization form
- HIPAA Research Authorization Form

- 8. Consent Personnel:** List the names of all members of the research team who will be obtaining consent/assent.

*[name] will be obtaining consent/assent*

- 9. Process of Consent/Assent:** Describe the setting and conditions under which consent/assent will be obtained, including parental permission or surrogate permission and the steps taken to ensure subjects' independent decision-making.

*The PI routinely consults with patients regarding urinary stones. During the initial outpatient consultation with the PI, patients who are candidates for ureterscopic management and are in agreement to this surgical method will be recruited to participate in the study. These are all patients being seen in the outpatient clinic prior to surgery and are not under any acute distress/pain.*

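### The enrolment target of 126 is exactly twice the 63 scored patients per arm that the formula needs, with no allowance for loss and no definition of who counts as enrolled

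*Combined protocol and SAP*

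**What the plan says.** The sample-size statement is in Section V, item 12 (Statistical Considerations). The design is "two independent groups with a continuous outcome (Pain measured on a 1-10 scale) and an enrollment ratio of 1". The inputs are "We anticipate mean post-operative pain in the non-intervention group to be 7 with a standard deviation of 2" and "We aim to detect a 10% difference in pain, in the intervention arm", and the result is "With an alpha of 0.05 and a power of 80% we will need to enroll 63 patients in each arm". The primary outcome is mean post-operative pain, with no time point named.

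Section VII, item 1 (Targeted Enrollment) gives the number "targeted for enrollment at Yale for this protocol 126".

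On the order of events, Section VII, item 9 (Process of Consent/Assent) says that at the initial outpatient consultation "patients who are candidates for ureterscopic management and are in agreement to this surgical method will be recruited to participate in the study". Item 10 of that section uses the word enrolled in connection with the consent discussion. Section V, item 3 (Research Plan) places randomization after eligibility and consent, and assigns it to the attending anesthesiologist.

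On data collection, the Research Plan schedules a pain rating at 1 hour, another at recovery-room discharge, a home survey and a one-week visit. Of the home survey it says: "This will be filled out once a day for a total of 7 days following the procedure".

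No section mentions cancellation, withdrawal, replacement or missing scores in connection with the sample size.

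**The concern.** A two-mean sample-size formula returns the number of patients whose outcome enters the comparison. It does not return the number approached, consented or randomized. The plan equates these quantities, so the power it states assumes complete data.

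There are two places where patients can drop out of the count. The first is between the clinic visit and the operating room, where an operation may be cancelled or changed. This matters only if consented patients count toward 126, which the plan leaves open. The second is between randomization and the primary score, which matters however 126 is defined.

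What is at stake is how a null result would be read. Section IX (Potential Benefits) says that a negative study would discourage use of the drug. A reader who takes the power to be 80% when it is lower would give such a result too much weight.

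**Working it through.** **Inputs.** Section V, item 12 gives SD 2, alpha 0.05, power 80%, 1:1 allocation and a control mean of 7. Sidedness is not stated; two-sided is assumed here. The difference in points is not stated. The loss rates below are assumptions, because the documents give none.

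**Step 1: reproduce 63.** The normal-approximation formula is n per arm = 2 x (1.96 + 0.8416)² x SD² / difference².

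- Difference 1.0: 2 x 7.849 x 4 / 1.00 = 62.8, so 63 per arm. This matches the plan.
- Difference 0.7 (10% of 7): 62.8 / 0.49 = 128.1, so 129 per arm. This does not match.
- Difference 0.9 (10% of the 9-point range from 1 to 10): 62.8 / 0.81 = 77.5, so 78 per arm. A one-sided test at 0.9 would give 62, close to 63 but not equal to it.

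The two-sided reading that gives 63 exactly is therefore 1.0 point, which is 10% of a 10-point scale but about 14% of the stated mean (1.0/7 = 0.143). The plan does not state this value. A t-test at 1.0 point needs 64 per arm.

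**Step 2: compare with the target.** 2 x 63 = 126, the figure in Section VII, item 1. The implied allowance for loss is zero.

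**Step 3: power at the number with a score.** Two-sample t-test, two-sided 0.05, SD 2, with n per arm = 63 x (1 - loss):

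| Assumed loss | Scored per arm | Power, 1.0 point | Power, 0.7 points |
|---|---|---|---|
| 0% | 63.0 | 79.5% | 49.6% |
| 5% | 59.9 | 77.4% | 47.6% |
| 10% | 56.7 | 75.2% | 45.5% |
| 15% | 53.6 | 72.7% | 43.4% |
| 20% | 50.4 | 70.0% | 41.3% |

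On the normal approximation at 1.0 point, power is 80.1% at 63 per arm, 79.8% after one loss (63 and 62) and 78.2% after six losses (60 and 60).

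**Step 4: what keeping 80% would take.** Per arm, the number to randomize is n / (1 - loss), rounded up. At 1.0 point, 63/0.90 = 70 and 63/0.80 = 78.75, so 79: totals of 140 and 158. At 0.7 points, 129/0.90 = 143.3, so 144, and 129/0.80 = 161.25, so 162: totals of 288 and 324.

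**Step 5: who counts toward 126.** The recruitment and consent items describe entry in clinic, and item 10 ties the word enrolled to consent. Section V, item 12 speaks of enrolling 63 patients in each arm, and a patient has an arm only after randomization. The text supports both readings and settles neither.

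**The case against.** A reader might infer that 126 counts patients consented in clinic, so that every cancelled operation costs power. The documents do not establish this. The consent items say where patients are recruited, not who counts toward the target, and the phrase about patients in each arm points to randomized patients. On that reading, a case cancelled before randomization costs nothing. The objection stands in full against treating clinic consent as the plan's rule; what remains is that the term is undefined.

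A reader might also infer that attrition is what takes the trial below 80%. That is too strong. At 1.0 point the t-test already gives 79.5% with no loss, and six losses cost only about two percentage points. On the plain reading of 10% of 7, power is about 50% with complete data, so the effect size is the larger problem and must be settled first.

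Heavy loss is not shown to be likely either. No primary time point is named. If it were the 1-hour or recovery-room score, taken on site, missing home forms would not affect it, and eligibility requires patients to be willing and able to complete all questionnaires. Equally, with no time point named, the plan cannot rely on those on-site scores to protect the primary comparison.

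Finally, 2 x 63 = 126 is correct arithmetic. The fault is that a number of scored patients is used as an enrolment number.

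**Conclusion.** The concern holds in a limited form. The number of scored patients required is used as the number to enrol, the total is exactly double it, and there is no allowance for loss. The stated 80% is met, and then only on the normal approximation at 1.0 point, if every one of the 126 is randomized and has a primary score.

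At 1.0 point the cost is about 2 percentage points of power at 5% loss, 4 at 10%, 7 at 15% and 9 to 10 at 20%. At 0.7 points, power falls from about 50% to about 46% and 41% at 10% and 20% loss. These figures rest on SD 2, a two-sided test, equal loss in both arms and assumed loss rates. The 1.0-point difference is inferred by working back from 63. This should be corrected, but it is secondary to reconciling the effect size.

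**What to change.** Make the changes in this order.

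1. In Section V, item 12, state the target difference in points and the sidedness, and reconcile the 10% difference with the mean of 7. If 1.0 point is intended, 63 per arm stands on the normal approximation. If 0.7 is intended, 63 does not give 80% power and the plan must say so or revisit the sample size.
2. In the same item, name the time point of the primary score and say that 63 per arm (or the figure that replaces it) is the number of patients with that score.
3. In Section VII, item 1, define 126 as patients randomized in the operating room, so that patients consented but never randomized do not use up places.
4. Restate the power at the expected number with a primary score, naming the difference and labelling the loss rate as an assumption. For example: with 126 randomized and a 1.0-point difference, about 75% if 10% have no primary score and about 70% if 20% have none. These figures should not be written in without that condition, because at 0.7 points they are about 46% and 41%.

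The cost is wording, a less favourable stated power, and a few more patients consented who are never randomized. No extra randomized patients are needed, because this corrects the claim and does not restore 80%. Restoring 80% would need the larger totals in the working.

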#### **A. DRUGS, BIOLOGICS and RADIOTRACERS**

- 1. Identification of Drug, Biologic or Radiotracer:** What is (are) the **name(s)** of the drug(s) biologic(s) or radiotracer(s) being used? Identify whether FDA approval has been granted and for what indication(s).

*Name of Drug: Ketorolac Tromethamine.*

*It has FDA approval as a nonsteroidal anti-inflammatory drug (NSAID), indicated for the short-term (up to 5 days in adults), management of moderately severe acute pain that requires analgesia at the opioid level.*

- 2. Background Information:** Provide a description of previous human use, known risks, and data addressing dosage(s), interval(s), route(s) of administration, and any other factors that might influence risks. If this is the first time this drug is being administered to humans, include relevant data on animal models.

Ketorolac has been used for roughly the past 20 years as an alternative to opiates for parenteral pain management. Limiting the duration of use to 5 days or less has been shown to reduce the adverse effects associated with long-term use (8). The adverse effects of ketorolac are similar to other NSAIDs, including gastrointestinal bleeding, peptic ulcers, renal failure in patients with chronic kidney disease, and bleeding due to platelet enzyme inhibition (9). To minimize the risk of bleeding, it is recommended not to administer ketorolac along with warfarin, heparin, or other NSAIDs (7).

The effects of analgesia with IV and IM administration of ketorolac is generally observed within 10 minutes, with peak pain control at 75-150 minutes. Current dosing recommendations for patients is 30 mg for a single dose, with totally daily dosages totaling less than 60 mg. Age related dosing for patients >65 years is generally accepted to be half of the dosage used for patients <65 years (7, 10).

Studies assessing the use of pre-operative IV administration of ketorolac demonstrated that 15-30 mg of ketorolac did not increase operative times or estimated blood loss, and also did not

significantly affect renal function. Ketorolac also decreased the use of morphine in the experimental group (11).

Other studies assessing the risk of bleeding in patients with concomitant use of ketorolac and anticoagulants failed to demonstrate any enhanced risk of operative site bleeding (8). There was a small risk of gastrointestinal bleeding noted in elderly patients who had used ketorolac more than 5 days with dosages exceeding 105 mg/day; however, use in patients younger than 65 years with dosages less than 105 mg/day, and usage for 5 days or less failed to show any increased risk of GI bleeding (12).

Bleeding risk with ketorolac has been established in spinal surgeries, where a single IV intra-operative dose of 30 mg failed to induce any significant changes in gross or surgical site bleeding (13).

3. **Source:** a) Identify the source of the drug or biologic to be used.

b) Is the drug provided free of charge to subjects?  Yes  No

If yes, by whom? This drug is routinely covered as a cost by insurance as part of pain management for outpatient procedures.

4. **Storage, Preparation and Use:** Describe the method of storage, preparation, stability information, and for parenteral products, method of sterilization and method of testing sterility and pyrogenicity. This drug is routinely utilized by Yale-New Haven hospital and is subjected to the same standards of storage and handling as other commonly utilized post-operative pain medication.

Check applicable Investigational Drug Service utilized:

